The concomitant elevation in CSF-1 serum levels and the increase in the serum levels of CK, LDH, and AST suggest pharmacodynamic activity of IMC-CS4. Since preclinical studies with IMC-CS4 in monkeys demonstrated a dose-response correlation between the dose of IMC-CS4 and the increase in serum enzyme levels, a dose escalation was considered likely to result in a DLT. Therefore, it was considered medically prudent not to dose escalate further as initially planned.

In order to better characterize the IMC-CS4 dose-response effect on the monocyte / macrophage system and on various serologic and hematologic parameters, the dosing scheme and schedule was amended in Protocol Amendment Version 3.0 to reflect dose reductions and prolonged administration intervals as follows: Under Version 2.0 of the protocol, dose escalation was to begin at 2.5 mg/kg in Cohort 1 and proceed to 5, 10, 20, and 30 mg/kg (all qw) in Cohorts 2 to 5, respectively. Following completion of Cohort 1 (2.5 mg/kg), the dose-escalation scheme was revised to 0.3 mg/kg qw in Cohort 2, 0.6 mg/kg qw in Cohort 3, 1.25 mg/kg every 2 weeks (q2w) in Cohort 4, 1.25 mg/kg qw in Cohort 5, and 2.5 mg/kg q2w in Cohort 6 (a newly added cohort). The addition of q2w dosing was deemed reasonable based on the relatively long half-life observed in cynomolgus monkeys.

Further rationale for the revised dose-escalation scheme was as follows. The second cohort started at approximately an 8-fold lower dose level (0.3 mg/kg administered qw) than the study starting dose (2.5 mg/kg qw in Cohort 1). Additionally, certain doses (1.25 and 2.5 mg/kg) were to be administered on both qw and q2w regimens to facilitate PK/PD characterization. Upon completion of all 6 planned cohorts, the PK/PD and safety profiles were to be evaluated to assess if further dose escalation and/or regimens were warranted to determine the recommended Phase 2 dose (RP2D).

1.4.3 Clinical Experience from Cohorts 2 through 5

This section describes the clinical experience after the revised dose-escalation scheme was implemented in Protocol Amendment Version 3.0, specifically, the clinical observations for Cohorts 2, 3, 4, and 5. No DLTs were observed in Cohorts 2 and 3. The clinical data generated for subjects treated in Cohorts 2 and 3 indicate that IMC-CS4 is safe and well tolerated when administered as 4 qw doses (0.3 or 0.6 mg/kg) followed by 2 weeks of recovery.

[figure not shown]

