3.1 Introduction

This statistical analysis plan for protocol CP24-1001 (I5F-IE-JSCA), Version 3.0, dated 28 March 2012, describes the detailed procedures for executing the planned statistical analyses for the clinical study report. Pharmacokinetic, pharmacodynamic and immunogenicity data will be analyzed by the ImClone LLC Clinical Pharmacology department.

The statistical analyses will be conducted by ImClone LLC or a contract research organization (CRO) using SAS® software Version 9.1.3 or higher.

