5.1.2 Safety Population

All enrolled subjects who received at least one dose of IMC-CS4 will be included in the Safety Population, regardless of their eligibility for the study. The Safety population will be used for the analysis of baseline characteristics, efficacy data and safety data.

5.1.3 ~~Maximum Tolerated Dose~~Dose Limiting Toxicity

~~(MTD-DLT)~~ Population

Subjects who complete the initial 6 weeks of therapy¹ or experience a DLT during the first cycle will be included in the ~~MTD-DLT~~ Population. Patients who discontinued during the initial 6 weeks due to reasons other than DLT will be excluded from the ~~MTD-DLT~~ population. The ~~MTD-DLT~~ population will be used for the evaluation of DLTs in order to determine the ~~MTDRP2D~~.

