5.2 Definitions and data handling conventions

5.2.1 Safety Data Handling and Definitions

5.2.1.1 Coding

- **Adverse events:** All adverse events (AE) will be coded by the Medical Dictionary for Regulatory Activities (MedDRA™) and graded according to the National Cancer Institute (NCI) Common Terminology Criteria for Adverse Events (CTCAE), Version 4.0 (version 4.0 includes all of the minor versions 4.0x).

¹ i.e. first four infusions completed, plus an observation period of 21 days after last dose in cycle 1 or entry into cycle 2 if start of cycle 2 occurs before completion of the 21 days observation.
IMC-CS4 (LY3022855)

- **Pre treatment Therapy and Concurrent Therapy:** Current medications, medications taken within 30 days prior to first dose of study therapy, prior cancer therapy will be coded using the WHOdrug.

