5.2.1.4 Study Drug Exposure

Exposure analyses will be based on the actual dose administered (in mg) and body weight (in kg) per the eCRF. The baseline body weight will be used for calculating the cumulative dose unless the subject's weight changes $\geq 10\%$. For subjects with a weight change $\geq 10\%$, the revised weight will be used from the time point of the change and onwards.

For analysis of dose exposure **across all cycles** the following definitions will be used:

- **Duration of cycle:**
 - **Patients discontinuing during first cycle:** Duration of cycles (in weeks)² = $(\text{Date of last dose} - \text{date of first dose} + 21) / 7$
 - **Patients discontinuing treatment after start of Cycle 2:** Duration of cycles (in weeks)³ = $(\text{Date of last dose} - \text{date of first dose} + 7) / 7$
- Duration of treatment:
 - **Patients discontinuing during first cycle:** Duration of treatment (in weeks)⁴ = $(\text{Date of last dose} - \text{date of first dose} + 7) / 7$

² 21 days added to duration of cycle because of a 2 week observation period after last dose in cycle 1 (ie, 21 days until the next dose).

³ 7 days added to duration of cycle because administrations are planned every week (starting from Cycle 2).

⁴ 7 days added to duration of treatment because administrations are planned every week. Duration of treatment does not include the 2-week observation period in Cycle 1.

- **Patients discontinuing treatment after start of Cycle 2:** Duration of treatment (in weeks)⁵ = Duration of cycle -14
- Cumulative dose (mg/kg) = Sum of all [administered dosages (mg) / baseline weight⁶ (kg)]
- Dose intensity (mg/kg/week) = Cumulative dose / Duration of treatment
- Planned weekly dose: Refer to Table 1: Planned Dose Regimens
- Relative dose intensity (%) = (Dose intensity / Planned weekly dose) * 100.
- Number of dose reductions: total number of reduction steps comparing the intended dose level before each infusion (as entered in the eCRF) to the protocol planned dose level as referenced in Table 2: General Dose Reduction Guidelines.
- Dose delay within a cycle: a dose is considered delayed if it is administered more than 3 days after the scheduled date relative to the previous administration.

Table 1: Planned Dose Regimens

Cohort	All cycles	Dosing Frequency
1	2.5 mg/kg	Weekly
2	0.3 mg/kg	Weekly
3	0.6 mg/kg	Weekly
4	1.25 mg/kg	Every 2 weeks
5	1.25 mg/kg	Weekly
6	2.5 mg/kg	Every 2 weeks

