For analysis of dose exposure **in Cycle 1 only** the same definitions as across all cycles will be used except the following:

- Duration of cycles (in weeks)⁷ = (Date of last dose – date of first dose+21) / 7
Or if start of cycles 2⁸ occurs before last dose of cycle 1 + 21 days:
Duration of cycles (in weeks)= (Date of start Cycle 2-date of first dose)/7

⁵ 14 days is subtracted from the duration of cycle because the 2-week observation period is excluded from the duration of treatment.

⁶ Except in case of weight change from baseline $\geq 10\%$ as described above.

⁷ 21 days added to duration of cycle, because of a 2-week observation period after last dose in Cycle 1 (i.e. 21 days until the next dose).

⁸ Start of Cycle 2 is defined as day of first infusion of Cycle 2.

- Cumulative dose (mg/kg) = Sum of [all administered dosages during cycle 1 (mg) / baseline weight (kg)]

Table 2: General Dose Reduction Guidelines

Cohort	Planned Starting dose	First Reduction	Second Reduction
1	2.5 mg/kg weekly	Discontinue IMC-CS4	-
2	0.3 mg/kg weekly	Discontinue IMC-CS4	-
3	0.6 mg/kg weekly	0.3 mg/kg weekly	Discontinue IMC-CS4
4	1.25 mg/kg every 2 weeks	0.6 mg/kg every 2 weeks	0.3 mg/kg every 2 weeks
5	1.25 mg/kg weekly	0.6 mg/kg weekly	0.3 mg/kg weekly
6	2.5 mg/kg every 2 weeks	1.25 mg/kg every 2 weeks	0.6 mg/kg every 2 weeks

Note: Actual dose levels entered in the CRF will be rounded to the nearest dose level listed in this table (e.g. any IMC-CS4 dose level >5 and < 7.5 mg/kg will be rounded to 5 mg/kg for the purpose of the dose reduction calculation). No dose reductions are allowed after a DLT. In the setting of non-life-threatening reversible Grade ≤ 3 IMC-CS4-related toxicities that do not meet the definition of a DLT, IMC-CS4 may be held (if appropriate in the opinion of the Investigator) for a maximum of 3 weeks, until resolution to Grade < 2 .

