5.3.4.3 Treatment Emergent Adverse events

Treatment-emergent AEs will be summarized by MedDRA® System Organ Class (SOC) and preferred term (PT), classified from verbatim terms. The incidence and percentage of subjects with at least one occurrence of a preferred term will be included, according to the most severe NCI-CTCAE grade. Causality (relationship to study drug) will be summarized separately. If more than one AE is recorded for a patient within any SOC or PT term, the patient will only be counted once on the most severe grade and the closest relationship to treatment.

AEs reported with a causal relationship of ‘possibly related’ and ‘probably related’ to study medication or ‘does not know’ will be considered related to study medication. Missing classifications concerning study medication relationship will be considered as related to study medication.

The following will be summarized using the Safety population for all AEs, and the MTD population for AEs with onset date in Cycle 1 (ie, within 21 days after last dose in Cycle 1 and prior to start of Cycle 2):

- All AEs,
- SAEs,
- NCI-CTCAE Grade 3 or higher AEs,
- Related AEs, SAEs, and NCI-CTCAE Grade 3 or higher AEs,
- AEs leading to dose modification, study medication discontinuation, and death will be summarized according to MedDRA® Preferred Terms.
- Duration of AE will be determined and included in listings along with action taken and outcome.

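### SAP 5.1.3 footnote 1 requires four infusions to enter the DLT population, which every-2-week Cohort 4 cannot reach in Cycle 1; against protocol Version 7.0, the 21-day event cut-off also closes about 6 days early for that cohort

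*SAP*

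**What the plan says.** - **Who is in the DLT population.** SAP 5.1.3 admits subjects who complete the first six weeks or have a first-cycle DLT, and adds that "Patients who discontinued during the initial 6 weeks due to reasons other than DLT will be excluded from" it. Footnote 1 explains completion as "first four infusions completed, plus an observation period of 21 days after last dose in cycle 1". A closing clause offers one alternative end point, namely "or entry into cycle 2 if start of cycle 2 occurs before completion of the 21 days observation". No cohort is named.
- **Which events count as Cycle 1.** SAP 5.3.4.3 (adverse events) and 5.3.4.4 (DLTs) both limit Cycle 1 to "within 21 days after last dose in Cycle 1 and prior to start of Cycle 2". These sections still use the population's former name, MTD population.
- **Where 21 days comes from.** Footnote 2 to SAP 5.2.1.4 reads "21 days added to duration of cycle because of a 2 week observation period after last dose in cycle 1". Footnote 7, on the Cycle 1 duration formula, gives the same reason.
- **Cohort 4.** SAP Tables 1 and 2 list it as 1.25 mg/kg every 2 weeks. Protocol Tables 1 and 3 (Version 7.0) give it two Cycle 1 infusions, in Weeks 1 and 3, then observation in Weeks 4 to 6 of a six-week cycle. Protocol 4.1 names this regimen as the Part A MTD and says extra subjects were enrolled to it.
- **Versions.** The SAP is written to "protocol CP24-1001 (I5F-IE-JSCA), Version 3.0, dated 28 March 2012". The protocol's dose rationale (in the text just before 1.4.3) records that Version 3.0 already set "1.25 mg/kg every 2 weeks (q2w) in Cohort 4".

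**The concern.** Four infusions and 21 days describe the Part A weekly schedule. Applied to an every-2-week cohort, they create two separate problems.

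First, the footnote and the text it explains disagree about the same subject. Someone in Cohort 4 who finishes six weeks without a DLT is in the population by the text and out of it by the footnote. Two programmers could therefore produce different DLT denominators for the regimen named as the Part A MTD.

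Second, under the current schedule the event cut-off falls before the cohort's observation period ends. A DLT in the last days of Cycle 1 is a DLT under protocol 4.1.4 and brings the subject into the population under 5.1.3, but 5.3.4.4 does not count it.

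In SAP 6.3, 13 tables use the DLT population: 14.3.1.1, the Cycle 1 version of 14.3.2, 14.3.6, and the ten tables 14.3.7.2 to 14.3.16.2. Listing 15.1 uses it too. Eleven of the 13 tables (14.3.6 and the ten adverse-event tables) also depend on the 21-day cut-off.

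**Working it through.** Conventions: an infusion in week w falls on Day 7(w − 1) + 1; Cycle 1 is Days 1 to 42; Cycle 2 is planned for Day 43; the cut-off is the last Cycle 1 dose day + 21.

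**The SAP's own figures, Part A weekly cohorts.** Doses fall on Days 1, 8, 15 and 22, so there are four infusions. The cut-off is 22 + 21 = Day 43, so no day is lost. Cycle 1 duration by SAP 5.2.1.4 is (22 − 1 + 21)/7 = 6.0 weeks. Both four infusions and 21 days reproduce.

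**Point 1, infusion count for Cohort 4.**
- Uninterrupted dosing every 2 weeks falls on Days 1, 15, 29 and 43, so at most three infusions fit in 42 days, whatever the protocol version.
- Under Version 7.0 the infusions are in Weeks 1, 3, 7, 9 and 11. The fourth is in Week 9, that is Day 57, in Cycle 2.
- The Cycle 2 clause does not help. Planned entry on Day 43 comes after the 21 days end on 15 + 21 = Day 36. With the ±3-day window, the latest cut-off is 18 + 21 = Day 39 and the earliest Cycle 2 start is Day 40, which is still after it.
- Illustration, assuming 1 DLT among 6 to 12 evaluable subjects: the text gives 1/6 (17%) to 1/12 (8%), and the literal footnote gives 1/1. With no DLT in 3 subjects, 0/3 becomes 0/0. If Cycle 2 infusions are allowed to count, subjects who reach Week 9 return to the denominator. The number of subjects with a DLT never changes, because a DLT admits the subject regardless.

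**Point 2, cut-off for Cohort 4 under Version 7.0.**
- The last Cycle 1 dose is on Day 15, so the cut-off is Day 36. Uncounted days are 37 to 42: 6 of 42, or 14%.
- With ±3 days on both the second dose and the Cycle 2 start: dose on Day 18 and Cycle 2 on Day 40 give 0 of 39 days; dose on Day 12 (cut-off Day 33) and Cycle 2 on Day 46 leave Days 34 to 45, which is 12 of 45, or 27%.
- For Part A weekly cohorts (±2 days) the worst case is dose on Day 20 (cut-off Day 41) and Cycle 2 on Day 45, leaving Days 42 to 44, which is 3 days.
- Cycle 1 duration for Cohort 4 is (15 − 1 + 21)/7 = 5.0 weeks, against a six-week cycle.

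**Dependence of point 2 on the version.** Version 3.0's Cycle 1 schedule for Cohort 4 is not in the documents. If it had three infusions (assumption), the last dose is on Day 29, the cut-off is Day 50, past Cycle 2 entry, and the gap is zero. With two infusions it is 6 days nominally.

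**The case against.** The best defence is that footnote 1 is leftover weekly text that nobody would apply to Cohort 4. The SAP title page still describes a weekly study, the main text of 5.1.3 gives the sensible answer, SAP 5.5 declares no departures from the protocol, and the current protocol 12.2 is neutral as to schedule. That makes the 1/1 denominator unlikely in practice. It does not remove the contradiction: the footnote is worded as the definition of completion, and a SAP should not leave the denominator to a programmer's guess.

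The second defence is that point 2 sets a 2012 SAP against a later schedule. This stands, and point 2 is conditional for that reason. It matters when this SAP, the only one supplied, is used or updated for Version 7.0.

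Third, little would be lost from view. Late events remain in the Safety-population adverse-event tables, Listing 15.1 states no 21-day limit, and the analyses are descriptive. This also stands and limits the consequence to the Cycle 1 tables.

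A reader might infer more. Because SAP 5.1.3 says the population serves the RP2D, one might conclude that dose escalation or the Part A MTD was affected. The documents do not support this: escalation follows protocol 4.1.1 and the review meetings in 12.8, neither of which uses the footnote. One might also read 14% of days as 14% of DLTs missed; no event dates are given, so that does not follow.

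**Conclusion.** Point 1 holds with high confidence and under any protocol version: the footnote's infusion count is impossible for Cohort 4 within Cycle 1 and contradicts the section it explains. The same is true of the SAP's own every-2-week Cohort 6, which the current protocol has dropped. Point 2 holds only against Version 7.0. There, 6 of 42 nominal Cycle 1 days (0 to 12 days with visit windows) fall outside the cut-off, and the duration formula gives 5.0 weeks where the cycle is 6.0.

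The effect on reported DLT denominators and Cycle 1 counts cannot be sized, because neither Cohort 4's enrolment nor its event dates are given. The rates shown rest on an assumed 1 DLT in 6 to 12 subjects. The SAP should be corrected, since these tables describe the named Part A MTD regimen.

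**What to change.** 1. **Footnote 1.** Define completion as having received every Cycle 1 infusion scheduled for the subject's cohort (as in protocol 12.2) and having been followed to the end of the six-week Cycle 1 (Day 42), including any observation period, or to entry into Cycle 2 if earlier. Naming Day 42 keeps the footnote in line with the six-week text in every cohort, including Part B cohorts, which have no observation period.
2. **5.3.4.3 and 5.3.4.4.** Replace the 21-day rule with onset from first dose until before the first Cycle 2 infusion. If Cycle 2 is not started within its dosing window, count to the later of Day 42 and the day before the cohort's planned interval from last Cycle 1 dose to Cycle 2 ends (21 days for Part A weekly, 28 days for every 2 weeks). Check: 22 + 21 − 1 = 42 and 15 + 28 − 1 = 42. The worst case above (Cycle 2 on Day 46) is now counted through Day 45.
3. **5.2.1.4.** Replace the fixed +21 days, in both places where it is used for Cycle 1 duration, with the same cohort interval. For Cohort 4, (15 − 1 + 28)/7 = 6.0 weeks. Change the 21-day condition on an early Cycle 2 start to match.
4. **On updating to Version 7.0.** Take Part B intervals from each cohort's schedule: 7 days for weekly cohorts (36 + 7 − 1 = 42) and 14 days for 6b, 7b and 8b (29 + 14 − 1 = 42).

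The cost is SAP wording and programming. Data collection and dosing do not change.

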5.2.1.2 Treatment-Emergent Adverse Events

An AE will be regarded as **treatment-emergent** if its onset date occurs any time after the administration of the first dose of study medication, up to 30 days after the last dose of study medication (or up to any time if related to study medication), or if it occurs prior to first dose date and worsens while on study medication.

5.2.1.3 Partial Dates for Adverse Events, Concomitant Medications and Birthday

For the patient data listings no imputation of incomplete dates will be applied. The listings will show the incomplete dates without any change. Dates with missing day or both day and month, will adhere to the following conventions:

- The missing day of onset of an adverse event or start date of a concurrent therapy will be set to:
 - The date of the first study treatment, if the onset year and month is the same as year and month of the first study treatment
 - First day of the month that the event occurred, if the onset year and month is after the year and month of first study treatment
 - The date of informed consent, if the onset month/year is before the month/year of the first study treatment.
 -
- If the onset date of an adverse event or start date of a concurrent therapy is missing both, day and month, the onset date will be set to:
 - The date of the first study treatment, if the onset year is the same as the year of the first study treatment
 - January 1 of the year of onset, if the onset year is after the year of the first study treatment

- The missing day of resolution of an adverse event or end date of a concurrent therapy will be set to the last day of the month of the occurrence. If the patient died the same month, then set the imputed date as the date of death.
- If the resolution date of an adverse event or end date of a concurrent therapy is missing both the day and month, the date will be set to:
 - December 31 of the year of occurrence. If the patient died the same year, then set the imputed date as the date of death.

Only year of birth is collected in the study. Age will be derived from year of birth by setting the date to 1 July of the year of birth.

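### SAP 5.2.1.3 moves a partial adverse event onset to the first-dose date without checking whether the event had already resolved

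*SAP*

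**What the plan says.** SAP Section 5.2.1.3 covers AE onsets and concurrent-therapy start dates alike: "The missing day of onset of an adverse event or start date of a concurrent therapy will be set to" one of three values.

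- Day missing, same month as first dose: "The date of the first study treatment, if the onset year and month is the same as year and month" of the first treatment.
- Day missing, later month: the first of the recorded month.
- Day missing, earlier month: "The date of informed consent, if the onset month/year is before the month/year of the first study treatment".

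With day and month both missing, the onset becomes "The date of the first study treatment, if the onset year is the same as the year of the first study treatment". None of these onset rules mentions the resolution date.

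The section exempts one type of output: "For the patient data listings no imputation of incomplete dates will be applied".

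SAP 5.2.1.2 calls an event treatment-emergent "if its onset date occurs any time after the administration of the first dose of study medication", within the follow-up limits given there, or if it began before dosing and worsened on treatment. It has no exclusion for an event that ended before dosing. SAP 5.3.4.3 selects the Cycle 1 AE summaries by onset date.

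**The concern.** Placing an ambiguous onset at first dose is a normal conservative convention. The difficulty arises when the onset is not ambiguous in the respect that matters. Protocol Section 9 has sites collect both onset and resolution dates, so the database may show that an event was over before the first infusion. The rule then discards that fact.

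Such events can occur. Protocol 12.5.2 has AEs assessed from consent, Protocol 8.1 requires AEs related to protocol procedures to be reported, and Protocol 7.1 requires a tumor biopsy within 7 days before first dose from Cohort 2 onward. A short biopsy-related event that ended before dosing, with its onset day unrecorded, is the plausible case.

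At stake is the accuracy of the treatment-emergent AE tables. Safety is a primary objective, and the cohorts are small enough for a single subject to be visible.

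**Working it through.** There is no sample-size or error-rate figure to reproduce. The check applies the written rules to dates. All calendar dates below are illustrative assumptions; the rules come from SAP 5.2.1.2 and 5.2.1.3, and the duration formula (end minus start plus 1, in days) from SAP 5.2.3.

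**General result.** Let F be the first-dose date and R a known resolution date with R ≤ F − 1. The rule sets onset to F, so duration = R − F + 1 ≤ 0. Every event of this kind receives an onset after its own resolution.

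**Worked cases under the SAP rules**

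- *Day missing, month matches.* First dose 20 May, resolved 5 May. Imputed onset 20 May; duration = 5 − 20 + 1 = −14 days.
- *Range for one month.* First dose 20 March, resolution on any day from 1 to 19 March: duration runs from 1 − 20 + 1 = −18 to 19 − 20 + 1 = 0 days.
- *Day and month missing, year matches.* First dose 20 March 2013, onset recorded only as 2013, resolved 15 January 2013. Imputed onset 20 March, 64 days after resolution; duration = −64 + 1 = −63 days.

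**Treatment-emergent status.** The imputed onset equals the first-dose date, and the definition requires that the "onset date occurs any time after the administration of the first dose of study medication". Two readings are possible:

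- First-dose day included: each event above is flagged treatment-emergent.
- Strictly later date required: none is flagged. But Protocol Section 9 lists onset dates, not times, so this reading would also drop genuine events dated to the day of first dose, including first-infusion reactions.

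The first reading is therefore the workable one, though the SAP does not state it.

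**Size.** One wrongly counted subject adds 1/n to an incidence: 1/3 = 33 percentage points in a cohort of 3, and 1/6 = 17 in a cohort of 6. These are upper limits. SAP 5.3.4.3 counts a subject once per preferred term, so the shift is zero if the subject has another qualifying event under that term.

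**Effect of a guard.** Take consent on 8 March 2013 and first dose on 20 March 2013, keep the imputed onset inside the recorded period and no later than a known resolution date, and use the first-dose or consent date only if it fits that window.

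- Onset March, resolved 12 March: the SAP gives 20 March and −7 days. The guard gives 8 March, 12 − 8 + 1 = 5 days, not treatment-emergent.
- Onset 2013 only, resolved 15 January: the guard gives 15 January, 1 day, not treatment-emergent.
- Control, onset March, resolved 28 March: both give 20 March and 28 − 20 + 1 = 9 days, so the conservative default is unchanged.

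**Consent-date rule.** With the same consent and first-dose dates, an onset recorded as January 2013 and resolved 10 February is moved to 8 March. The known month is overwritten and the duration is −26 + 1 = −25 days, but the event stays before first dose and is not treatment-emergent.

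**The case against.** The strongest reply is that the default errs in the safe direction: when timing is unknown, over-counting treatment-emergent events is better than missing them. That stands as a defence of the default. It does not cover the case where the resolution date has already settled the question. The same section caps imputed end dates at the date of death, so a guard of this type is already accepted practice in this SAP.

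A second reply is that several conditions must coincide: an AE that began and ended before dosing, an incomplete onset date, a resolution date that shows it, and a first dose in the matching month or year. That also stands, and it is why the frequency is probably low.

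Three stronger readings are tempting, and the documents do not support them.

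- *The consent-date rule and the false durations distort the reported safety profile.* Listings keep the raw partial dates. Concurrent therapies appear only in Listings 16.1 and 16.2. AE duration is likewise planned for listings only: "Duration of AE will be determined and included in listings along with action taken and outcome". No table in SAP 6.3 reports it. Moving a pre-dose onset to consent normally leaves it before first dose, so treatment-emergent status does not change. Pre-existing conditions are recorded as history (Protocol 6.2 and 8.1), not governed by this rule.
- *Misdated events certainly become treatment-emergent.* That depends on how the first-dose day is read, which the SAP leaves open.
- *Dose escalation could be affected.* DLTs are drug-related Cycle 1 events considered at safety review meetings (Protocol 4.1.4 and 12.8). Nothing shows that those decisions use imputed dates.

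**Conclusion.** The point holds in a narrow form. For an AE with a partial onset matching the month of first dose (or only the year, when the month is missing) and a resolution date before first dose, SAP 5.2.1.3 produces an impossible onset. On the workable reading of SAP 5.2.1.2, the event is then a false treatment-emergent event in the overall and Cycle 1 tables.

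The error is certain for each such record, but the documents give no count of them. The ceiling of 33 or 17 percentage points assumes one affected subject, a cohort of 3 or 6, and no other qualifying event for that term in that subject. This is a minor defect in a programming rule. It does not show that the date rules as a whole are unsound.

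**What to change.** In SAP 5.2.1.3, add: if the full or partial resolution date shows that an event ended before first dose, the imputed onset may not be later than the resolution date, and the event is not treatment-emergent. In SAP 5.2.1.2, state whether an onset on the first-dose date counts as treatment-emergent.

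As a tidy-up with no effect on the planned tables, use the consent date for an earlier-month onset only when consent falls in the recorded month; otherwise keep the imputed date within that month. Always using the first of the month would not be better: with consent on 8 March, first dose on 2 April and onset in March, it would date the event to 1 March, before consent. The same edit could supply the missing rule for a year-only onset before the year of first dose.

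The cost is two or three sentences and minor programming, with no new data. The SAP was written for protocol Version 3.0 and its dose table has no Part B cohorts, so it needs updating in any case.
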